8 STUDY OBJECTIVES

8.1 **Primary Objective(s)**

The primary objective of this study is to evaluate the contraceptive efficacy of 15 mg E4/3 mg DRSP using the Pearl Index in subjects aged 16 to 35 years, inclusive, at the time of screening.

8.2 Secondary Efficacy Objective(s)

The secondary objectives of this study are:

- 1. To evaluate the contraceptive efficacy of 15 mg E4/3 mg DRSP using the method failure Pearl Index and life-table analysis in subjects aged 16 to 35 years, inclusive, at the time of screening.
- 2. To evaluate the contraceptive efficacy of 15 mg E4/3 mg DRSP using the Pearl Index, the method failure Pearl Index and life-table analysis in the overall study population.

8.3 Other Secondary Objective(s)

- 1. To evaluate cycle control and bleeding pattern associated with 15 mg E4/3 mg DRSP.
- 2. To evaluate general safety of 15 mg E4/3 mg DRSP.
- 3. To evaluate the impact of 15 mg E4/3 mg DRSP on physical, psychological, and social functioning and well-being.
- 4. To assess the effect of various individual characteristics/ covariates (body weight, race, smoking, and fed/fasted condition) on the PKs of 15 mg E4/3 mg DRSP (Population PK Substudy).

9 INVESTIGATIONAL PLAN

9.1 Overall Study Design and Plan

This study is a multicenter, open-label, single-arm study.

The total duration of the study, including the screening, will range from 387 to 467 days for the participating subjects, which is approximately a year and one month. Those subjects who discontinue due to a pregnancy wish will be followed-up for a maximum of one year after study discontinuation for return of spontaneous menstruation and until pregnancy or initiation of a contraceptive method (whichever occurs first).

Approximately 2000 healthy female subjects at risk for pregnancy, between 16 and 50 years old (inclusive, at the time of screening), and requesting contraception will be enrolled in the study and initiate the investigational product. In total, 1800 subjects will be 16 to 35 years old (inclusive). Recruitment may be stopped when 2000 subjects have initiated the investigational product if the required number of subjects for the primary analysis (1800 subjects in the age group up to 35 years) has been reached. Recruitment in the age group > 35 years will be stopped when 200 subjects have initiated the investigational product.

Eligible subjects will be treated with 15 mg E4/3 mg DRSP for up to 13 consecutive cycles. The treatment must be taken once daily at approximately the same time of the day in a 24/4-day regimen, i.e. 24 active tablets followed by 4 placebo tablets (4-day hormone free interval).

The primary objective of the study is to evaluate the contraceptive efficacy of the new COC, using the Pearl Index calculation (which reflects the pregnancy rate associated with a contraceptive method) among the subjects aged 16 to 35 years inclusive.

The contraceptive efficacy will also be evaluated using the method failure Pearl Index (which reflects the pregnancy rate due to method failure only) and life-table analysis in the subjects aged 16 to 35 years inclusive and in the overall study population.

The general safety will be evaluated by the determination of routine laboratory parameters, vital signs, by performing physical, gynecological and breast examinations and by recording number, frequency, type and intensity of AEs and serious adverse events (SAEs).

Participating subjects will be asked to record daily in a subject diary their bleeding/spotting episodes. This will allow evaluating the bleeding pattern and the cycle control associated with the investigational product.

[figure not shown]
Treatment compliance will be assessed using data from the subject diary across the entire study and by cycle. The subject diary will also be used to determine whether or not a cycle is at risk for the Pearl Index calculation.

Amendment Final Version 1.1

FST*w***TRA**

Population PK will be assessed using plasma E4 and DRSP concentration data from a subset of approximately 500 subjects to address the relationship between E4 and DRSP PK parameters and various individual characteristics (e.g., body weight, race, smoking, and fed/fasted condition). Blood samples for PK analysis will be obtained at Visits 3 and 4 between Days 10 and 14 of Cycles 2 and 4 (see Section 9.6.4.2).

9.2 Rationale for Study Design

The design of this study is in line with the final minutes of the Advisory Committee for Reproductive Health Drugs meeting (FDA)³ held on January 23 and 24, 2007, the recommendations made by Kapp et al.⁴ and the requirements of the European Medicines Agency (EMA) and the EMEA/CPMP/EWP/519/98 Rev 1 Guideline on Clinical Investigation of Steroid Contraceptives in Women⁵ which states that:

- Studies including an active comparator are not generally requested for efficacy purposes;
- The duration of efficacy studies should be six months to one year or more;
- For any new contraceptive, at least 400 women should have completed one year of treatment.

This study is a multicenter, open-label, single-arm study which will allow quantification of the efficacy of the investigational product by calculating the pregnancy rate. The size of the study is also adequate to allow an assessment of the general safety and bleeding profile associated with the investigational product.

The study design was discussed with FDA during end of phase 2 meeting as well as EMA during scientific advice (EMA/CHMP/SAWP/629721/2012).

9.3 Selection of Study Population

This study will include healthy female subjects at risk for pregnancy, between 16 and 50 years old (inclusive) at the time of screening, and expressing the need for and desire to use contraception for at least 13 consecutive cycles.

The following eligibility criteria will be checked at Visit 1 and Visit 2 (see Sections 9.5.1 and 9.5.2).

9.3.1 Inclusion Criteria

A subject will be considered for inclusion in the study if she meets all of the following criteria:

- 1. Heterosexually active female at risk for pregnancy and requesting contraception.
- 2. Negative serum pregnancy test at subject screening.
- 3. Aged 16 to 50 years (inclusive) at the time of signing the informed consent (IC).
- 4. Willing to use the investigational product as the primary method of contraception for 13 consecutive cycles.
- 5. Good physical and mental health on the basis of medical, surgical and gynecological history, physical examination, gynecological examination, clinical laboratory, and vital signs.
- 6. Body mass index (BMI) below or equal to (\leq) 35.0 kg/m².
- 7. Able to fulfill the requirements of the protocol and have indicated a willingness to participate in the study by providing written IC.
- 8. Willing and able to complete the diaries and questionnaires.

9.3.2 Exclusion Criteria

A subject will be excluded from participation if she meets any of the following criteria:

[figure not shown]
- 1. For subjects who are not using hormonal contraception at screening, a menstrual cycle length shorter than 21 days or longer than 35 days.
- 2. Clinically relevant abnormal laboratory result at screening in the opinion of the investigator with an understanding of the central laboratory normal range.
- 3. Known hypersensitivity to any of the investigational product ingredients.
- 4. Currently pregnant or with the intention to become pregnant during the course of the study.
- 5. Currently breastfeeding or before two spontaneous menstruations have occurred after cessation of breastfeeding prior to start of trial medication.
- 6. Less than 6 weeks since last delivery/2nd trimester of abortion and before spontaneous menstruation has occurred following a delivery or 2nd trimester of abortion.
- 7. Smoking nicotine-containing products if \geq 35 years old.
- 8. Dyslipoproteinemia requiring active treatment with antilipidemic agent.
- 9. Diabetes mellitus with vascular involvement (nephropathy, retinopathy, neuropathy, other) or diabetes mellitus of more than 20-year duration.
- 10. Any arterial hypertension (controlled and uncontrolled) defined by blood pressure values of:
 - a. systolic blood pressure \geq 140 mmHg and/or,
 - b. diastolic blood pressure \geq 90 mmHg.
- 11. Personal history of deep vein thrombosis or pulmonary embolism.
- 12. Current prolonged immobilization or major surgery with prolonged immobilization planned in the next 12 months.

EST*w***TRA**

- protein C, and antithrombin deficiencies). 14. Current treatment with anticoagulants.
- 15. Presence or history of arterial thromboembolism (e.g. angina pectoris, ischemic heart disease, cerebral stroke or transient ischemic attack).
- 16. Complicated valvular heart disease (pulmonary hypertension, atrial fibrillation, subacute bacterial endocarditis).
- 17. History of pregnancy-related cardiomyopathy or moderately or severely impaired cardiac function.
- 18. Systemic lupus erythematosus.
- 19. Presence or history of migraine with aura at any age or migraine without aura if \geq 35 years old.
- 20. Within the past 6 months, has had undiagnosed (unexplained) abnormal vaginal bleeding, or any abnormal bleeding that is expected to recur during the trial (e.g., bleeding from cervical polyp, recurrent bleeding after sex).
- 21. In case of Chlamydial or gonococcal infection at screening, when no treatment initiated at subject enrollment.
- 22. Abnormal Pap test (written documentation of prior test or test at screening exam) based on the following criteria:
 - Pap test in the past 18 months with ASC-US unless:
 - o less than 21 years of age; or
 - a repeat Pap test at least 6 months later was normal; or
 - reflex HPV testing was performed and was negative for high-risk oncogene human-papilloma-virus (HPV).
 - Pap test in the past 18 months with LSIL unless less than 21 years of age.
 - Pap test in the past 18 months with ASC-H, atypical glandular cells, HSIL or malignant cells.
- 23. Presence of an undiagnosed breast mass.
- 24. Current symptomatic gallbladder disease.
- 25. History of COC-related cholestasis.
- 26. Presence or history of severe hepatic disease as long as liver function values have not returned to normal.
- 27. Presence or history of pancreatitis if associated with hypertriglyceridemia.
- 28. Porphyria.
- 29. Presence or history of hepatocellular adenoma or malignant liver tumors.
- 30. Renal impairment (GFR $\leq 60 \text{ mL/min}/1.73\text{m}^2$).
- 31. Hyperkaliemia or presence of conditions that predispose to hyperkaliemia such as renal impairment, hepatic impairment, adrenal insufficiency and women receiving daily, long-term treatment for chronic conditions or diseases with medications that may increase serum potassium concentration (e.g. ACE inhibitors, angiotensin-II receptor antagonists, potassium-sparing diuretics, potassium supplementation, heparin, aldosterone antagonist and non-steroidal anti-inflammatory drugs).

FST*w***TRA**

- 33. Presence or history of hormone-related malignancy.
- 34. History of non-hormone-related malignancy within 5 years before screening. Subjects with a non-melanoma skin cancer are allowed in the study.
- 35. Current regular use or regular use within 1 month prior to subject enrollment of drugs potentially triggering interactions with COCs including but not limited to:
 - Cytochrome P450 3A4 (CYP 3A4) inducers: barbiturates, primidone, bosentan, felbamate, griseofulvin, oxcarbazepine, topiramate, carbamazepine, phenytoin, rifampicin, St John's wort.
 - CYP 3A4 inhibitors: azole antifungals, phenylbutazone, modafinil, cimetidine, verapamil, macrolides, diltiazem and grapefruit juice.
 - Human immunodeficiency virus (HIV)/Hepatitis C virus (HCV) protease inhibitors and non-nucleoside reverse transcriptase inhibitors.
- 36. Use of an injectable hormonal method of contraception within 10 months (300 days) prior to screening of an injection with a 3-month duration, within 6 months (180 days) prior to screening of an injection with a 2-month duration, within 3 months (90 days) prior to screening of an injection with a 1-month duration.
- 37. History of alcohol or drug abuse (including laxatives) within 12 months prior to screening.
- 38. Any prior procedure, disease or condition that could result in altered absorption, excessive accumulation, impaired metabolism, or altered excretion of the investigational product.
- 39. Uncontrolled thyroid disorders.
- 40. Participation in another investigational drug clinical study within 1 month (30 days) or have received an investigational drug within the last 3 months (90 days) prior to study entry. Subjects who participated in an oral contraceptive clinical study, using FDA/EU approved active ingredients, may be enrolled 2 months (60 days) after completing the preceding study.
- 41. Sponsor, CRO or Investigator's site personnel directly affiliated with this study.
- 42. Is judged by the Investigator to be unsuitable for any reason.

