4.3 Predetermined Subgroups

The key subgroup in this study is subjects aged 16 to 35 years, inclusive, at the time of screening. This subgroup is used for the primary efficacy population. All data regarding disposition, baseline characteristics, compliance, exposure and contraceptive efficacy will be presented for subjects aged 16 to 35 years and for all subjects within the specified analysis population.

In addition, subgroup analyses will be performed for the Pearl Index and bleeding data (specifically unscheduled bleeding and spotting and the absence of scheduled bleeding) for the following categories:

- Body Mass Index (BMI) categories (< 30, ≥ 30 kg/m²) at Baseline
- Race category (White, Black or African American, Asian, American Indian or Alaska Native, Native Hawaiian or other Pacific Islander, Other Race)
- Starters (including true new users)/Switchers (see Section 5.5)

- Smokers/Non-smokers at Baseline
- Age (\geq 16 to \leq 25; > 25 to \leq 35 and > 35 years old) at Screening

The non-smokers group includes subjects who are former smokers and never smokers. The smokers group includes subjects who are current smokers. The other race group includes subjects who selected more than one race or whose race was recorded as other race on the CRF.

Quality of life data will be presented for all subjects and for starters and switchers separately.

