The descriptive statistics (e.g., mean, SD, median, minimum, and maximum) for the number of unscheduled bleeding and/or spotting days, bleeding days, and spotting days within a cycle will also be summarized in subjects who experienced an unscheduled bleeding and/or spotting episode within that cycle. This will be presented for the classical and modified analysis in the ITT and PP Populations. Additionally, unscheduled bleeding and spotting and the absence of scheduled bleeding will be summarized for all subgroups specified in Section 4.3 by cycle for the classic cycle analysis for the ITT, PP Population and the PP Population excluding cycles with at least 1 missed active pill and the modified cycle analysis for the ITT Population.

The number and percentage of subjects with a scheduled bleeding episode starting on each day in the scheduled bleeding period in the shifted cycle (i.e. Day 25, 26, 27, 28 and Day 1, 2 and 3 of the next cycle in the diary) will be summarized by Cycle. If there is more than one scheduled bleeding episode, then the only the earliest start date of the scheduled bleeding episodes starting within the cycle will be counted. This will be presented for the classical and modified analysis in the ITT Population.

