9.8.4 Prespecified Hypotheses

Pre-specified hypotheses will be tested before any hypotheses that are based on diagnostic plots. Formal conclusions will be drawn only from these prespecified hypotheses. Results of other hypotheses (e.g., those based on diagnostic plots) will be considered exploratory and will not lead to conclusions.

- 1. Effect of body weight on volume of distribution of E4.
- 2. Effect of body weight on clearance of E4
- 3. Effect of race on clearance for E4.
- 4. Effect of smoking status on clearance for E4.

Protocol no: MIT-Es0001-C302

- 5. Effect of fed vs fasted state on rate (e.g. Ka) or extent (e.g., F) of absorption for E4.
- 6. Effect of body weight on volume of distribution of DRSP.
- 7. Effect of body weight on clearance of DRSP
- 8. Effect of race on clearance of DRSP.
- 9. Effect of smoking status on clearance of DRSP.
- 10. Effect of fed vs fasted state on rate (e.g. Ka) or extent (e.g., F) of absorption for DRSP.

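### Smokers are excluded from age 35, so the all-age bleeding tables by smoking and the two smoking hypotheses in the PK analysis are partly confounded with age

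*Protocol*

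**What the plan says.** Protocol 9.3.2, criterion 7, excludes women for "Smoking nicotine-containing products if \geq 35 years old". Protocol 9.3.1 admits women from 16 to 50, and Protocol 9.1 caps the older group: "Recruitment in the age group > 35 years will be stopped when 200 subjects have initiated the investigational product".

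SAP 4.3 lists "Smokers/Non-smokers at Baseline" as a subgroup and states that "The smokers group includes subjects who are current smokers"; former and never smokers form the other group. Age is a separate one-way subgroup and is not crossed with smoking.

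SAP 6.4 presents bleeding data for all subjects. SAP 9.5.3.1 adds that "unscheduled bleeding and spotting and the absence of scheduled bleeding will be summarized for all subgroups specified in Section 4.3 by cycle", in four versions: classical ITT, PP, PP without missed active pills, and modified ITT. Pearl Index subgroups (SAP 9.5.1) are limited to ages 16 to 35.

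In SAP 9.8.4, hypothesis 4 is "Effect of smoking status on clearance for E4" and hypothesis 9 is its DRSP counterpart. On their status: "Formal conclusions will be drawn only from these prespecified hypotheses". None of the ten hypotheses concerns age. SAP 9.8.11 names weight, race, smoking and fed/fasted status as covariates, leaves that list open, and allows an automated covariate search afterwards. It sets p<0.05 for forward addition and p<0.001 for backward elimination.

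**The concern.** An eligibility rule, and not chance, has tied one factor of interest to another. The smoker group stops at age 34. The non-smoker group holds everyone aged 35 and the up to 200 women aged 36 to 50. If bleeding or clearance varies with age, part of that variation will appear as a difference between smokers and non-smokers. A larger sample does not reduce this bias; it only makes a spurious difference easier to detect.

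The PK analysis matters most, because hypotheses 4 and 9 are among the few results in the trial that may carry a formal conclusion. For bleeding, the age table and the smoking table sit side by side, but no planned table separates the two factors.

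**Working it through.** The plan gives no figure on this point, so the size has to be worked out from assumptions.

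**Inputs from the documents:** 1800 women aged 16-35, at most 200 aged over 35, about 500 in the PK substudy, no smokers aged 35 or over, and p-value thresholds of 0.05 and 0.001.

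**Assumed, because the documents do not give them:** ages even over 16-35; mean age 42 in the 200 older women; 10-25% smokers among women under 35; a PK subset with the trial's age mix; an age slope in clearance of 0.3-1% per year; a between-subject CV of 25-35%.

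**Age structure.** 1800/20 = 90 women per year of age. That gives 19 × 90 = 1710 women under 35 (mean age 25) and 90 + 200 = 290 aged 35 or over. The mean age of the 290 is (90 × 35 + 200 × 42)/290 = 39.8, which is 14.8 years above the younger women.

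**Leakage.** With smoking fraction p under 35, non-smokers number 2000 − 1710p and the share aged 35 or over is 290/(2000 − 1710p). The mean-age gap between the groups is that share × 14.8 years. A 10-point age difference in bleeding (35 or over versus under 35) shifts the smoking contrast by share × 10 points.

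| Smokers under 35 | Smokers | Non-smokers | Non-smokers aged 35+ | Mean-age gap (years) | Shift per 10 points |
|---|---|---|---|---|---|
| 10% | 171 | 1829 | 15.9% | 2.35 | 1.6 |
| 15% | 256.5 | 1743.5 | 16.6% | 2.47 | 1.7 |
| 25% | 427.5 | 1572.5 | 18.4% | 2.73 | 1.8 |

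The share is not very sensitive to these choices. With 5-30% smokers, and 35-year-olds making up 0-5% of the 16-35 group, it runs from 10.5% to 19.5%.

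**PK.** Bias = age gap × slope. SE = CV × √(1/n₁ + 1/n₀), with the group sizes scaled to 500. With z = bias/SE and c = 1.96 or 3.29, the false-positive rate is 1 − Φ(c − z) + Φ(−c − z).

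| Smokers, slope, CV | n₁ / n₀ | Bias | SE | z | At p<0.05 | At p<0.001 |
|---|---|---|---|---|---|---|
| 10%, 0.3%/yr, 35% | 43 / 457 | 0.71% | 0.056 | 0.13 | 5.2% | 0.11% |
| 15%, 0.5%/yr, 30% | 64 / 436 | 1.23% | 0.040 | 0.31 | 6.1% | 0.16% |
| 25%, 1%/yr, 25% | 107 / 393 | 2.73% | 0.027 | 1.00 | 17.1% | 1.1% |

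This SE treats each woman's clearance as known exactly. SAP 9.8.1 describes the data as very sparse (two samples at each of two visits), so the true SE is larger and the inflation smaller.

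**Pearl Index by smoking.** Only the 35-year-olds are affected. They are 90/(1800 − 171) = 5.5% to 90/(1800 − 427.5) = 6.6% of the non-smokers in that table.

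**The case against.** The strongest reply is that most of the comparison is sound. More than 80% of non-smokers fall in the age range that smokers also cover. A reader might infer that any age difference will be reported in full as a smoking effect; the figures do not support that, since only about one-sixth leaks through. This part of the objection stands.

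The second reply concerns thresholds. A reader might take 17% as the false-positive rate for hypotheses 4 and 9. That is the least favourable combination at the forward step. Under SAP 9.8.11 an effect must also survive backward elimination at p<0.001, where the same inputs give at most 1.1%. This also stands, although 1.1% is eleven times the nominal 0.1%.

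Third, a reader might infer that the PK model shuts age out. It does not: the covariate list is open, and if age enters, smoking can be re-tested with age in the model. But nothing requires age to enter. The prespecified hypotheses are tested first, the automated search is conditional, and other hypotheses are exploratory. So this reply only partly answers the concern.

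Fourth, SAP 9.0 plans no formal statistical analyses, so the bleeding tables carry no test. Nor do the documents report any effect of age on bleeding or clearance, so the bias is conditional on one existing. Both points stand and hold the severity down.

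**Conclusion.** The imbalance is certain from the eligibility rule, deviations aside. Its consequence is limited. On the assumptions above, the smoking contrast absorbs about 16-18% of any difference between women aged 35 or over and younger women. In PK that means a spurious clearance effect of about 0.7-2.7%, with false-positive rates of about 5-17% at the forward step and 0.1-1.1% at the backward step. Smoking prevalence, the age slope, the CV and the age mix of the PK subset are all assumed.

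Severity is low. The primary endpoint and the sample size are not affected. The case for a change rests mainly on the two formal PK hypotheses, because the bias is built in by design and cheap to remove.

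**What to change.** - **SAP 4.3 and 9.5.3.1:** present the smoker/non-smoker bleeding tables in women under 35 at screening.
- **SAP 9.8.4 and 9.8.11:** name age as a prespecified covariate that is in the model when hypotheses 4 and 9 are tested, or test or repeat those hypotheses in women under 35. Restriction is the cleaner option, since an age term has no smokers to draw on from 35 upwards.
- **Pearl Index by smoking:** restriction to under 35 is optional, since only about 6% of its non-smokers are affected.

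This removes the imbalance that the exclusion creates. It does not remove any age difference between smokers and non-smokers within 16-34.

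The cost is SAP wording, because age is already collected. No smokers are lost. About 16-18% of non-smokers leave the smoking comparison (290 women in the full trial, or 290/4 ≈ 72 in the PK subset under the same age mix). At 15% smokers this changes n₀ from 436 to about 363 and raises the SE of the PK contrast by about 1%: √[(1/64 + 1/363)/(1/64 + 1/436)] ≈ 1.01.

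### Exclusion 10 says it covers controlled hypertension, but its only stated test is a reading of 140/90 mmHg or more, which a woman controlled on treatment does not meet

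*Protocol*

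**What the plan says.** Protocol 9.3.2 no. 10 excludes "Any arterial hypertension (controlled and uncontrolled) defined by blood pressure values of" at least 140 mmHg systolic and/or at least 90 mmHg diastolic. The Synopsis has the same text. Neither copy mentions a diagnosis, a history of hypertension or antihypertensive treatment.

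On timing, section 9.3 states: "The following eligibility criteria will be checked at Visit 1 and Visit 2". Section 9.6.3.7 has blood pressure taken seated, after at least five minutes of rest, at Screening and at every visit from 2 to 7.

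Two other exclusions catch some blood-pressure drugs for different reasons:

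- No. 31 concerns raised potassium. Its examples of daily long-term medication are "ACE inhibitors, angiotensin-II receptor antagonists, potassium-sparing diuretics, potassium supplementation, heparin, aldosterone antagonist and non-steroidal anti-inflammatory drugs".
- No. 35 concerns interactions with combined oral contraceptives (COCs). It includes "CYP 3A4 inhibitors: azole antifungals, phenylbutazone, modafinil, cimetidine, verapamil, macrolides, diltiazem and grapefruit juice".

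What remains is general. Inclusion 5 asks for "Good physical and mental health on the basis of medical, surgical and gynecological history", and also on examinations, laboratory results and vital signs. Exclusion 42 applies to a woman who "Is judged by the Investigator to be unsuitable for any reason". Section 7.2 says that the usual COC contraindications apply, without listing them.

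**The concern.** The lead-in of no. 10 and its test point to different women. Hypertension controlled below 140/90 mmHg does not, at the visit, produce the values that the criterion uses to define it. Site staff who compare the visit reading with the two limits would record no. 10 as not met. Staff who read the limits as a definition of the underlying disease would exclude the same woman.

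What is at stake is who receives an investigational COC and who enters the safety population. The protocol gives hypertension its own exclusion, and section 9.6.4.6 records it as a cardiovascular risk factor, but that section attaches no eligibility consequence. The study may use up to about 80 centers, so the same treated woman could be accepted at one and refused at another. No blood-pressure stopping threshold is stated for the treatment period, so the entry criterion is the only place where the protocol sets a fixed blood-pressure limit.

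**Working it through.** There is no figure to reproduce. The check applies each relevant rule to one illustrative woman: diagnosed hypertension, on daily long-term treatment, reading 126/78 mmHg at both Visit 1 and Visit 2. Since 126 < 140 and 78 < 90, neither limb of no. 10 is met by her readings. Only her drug is varied.

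| Rule | ACE inhibitor | Verapamil | Thiazide |
|---|---|---|---|
| No. 10, limits applied to visit readings | not excluded | not excluded | not excluded |
| No. 10, limits read as defining the disease | excluded | excluded | excluded |
| No. 31 (potassium) | excluded | not named | not named |
| No. 35 (interaction) | not named | excluded | not named |
| Inclusion 5, no. 42, section 7.2 | judgement | judgement | judgement |

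For the first two drugs, another fixed rule removes her whichever way no. 10 is read. For the third, the outcome depends on the reading of no. 10 and then on judgement.

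**How much nos. 31 and 35 cover.** No. 31 names four classes used for blood pressure: ACE inhibitors, angiotensin-II receptor antagonists, potassium-sparing diuretics and aldosterone antagonists. No. 35 names two such drugs, verapamil and diltiazem. That gives 4 + 2 = 6 named entries. Both lists are open-ended, but an unnamed drug is caught only if it raises potassium or interacts with the COC, not because it treats hypertension.

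**What the drafting of neighbouring criteria shows.**

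- No. 39 reads "Uncontrolled thyroid disorders". The list therefore limits a criterion to uncontrolled disease when that is the aim. By contrast, the bracket in no. 10 was probably meant to exclude treated women as well.
- No. 8 reads "Dyslipoproteinemia requiring active treatment with antilipidemic agent". The list also contains a criterion that turns on treatment. No. 10 has no such limb.

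The probable intent is therefore clear from context, but the stated test does not deliver it.

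**The case against.** The strongest reply is that the excluding reading is the natural one. If 140/90 defines the disease, every word of no. 10 has effect; if it applies only to the visit readings, the word *controlled* does nothing. There are also backstops. Section 9.3 limits the study to healthy women. Inclusion 5 is mandatory and looks to the medical history, which includes hypertension. Section 7.2 signals caution, and section 13.1 sends site questions to the sponsor's representative. After entry, blood pressure is measured at each scheduled visit, clinically significant findings become adverse events, and 13.4 allows withdrawal for safety.

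Most of this stands. It makes the problem narrow and makes wrongful entry less likely. It does not remove the problem, because each backstop is a judgement or a query route, whereas the one fixed rule on hypertension states a test that the treated woman passes.

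Three stronger readings are tempting, and the documents do not support them:

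- A reader might infer that the protocol plainly admits treated women. It does not; the lead-in points the other way.
- A reader might infer from 13.4 that thromboembolic events are the only compulsory reason to stop. Pregnancy also ends treatment and participation (9.6.2.2 and 13.4). The supportable statement is only that no blood-pressure stopping threshold is given.
- A reader might infer that sites did enrol differently. The documents show the scope for that, not that it happened.

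**Conclusion.** The point holds as a wording defect with a safety-eligibility consequence. It should be corrected, but it does not threaten the trial's conclusions.

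The women affected have current hypertension and read below 140/90 mmHg at both eligibility visits. They are either untreated or on a drug outside the six named entries and not otherwise caught by nos. 31 or 35. Their number cannot be estimated from the documents. Neither the Pearl Index calculation nor the sample size depends on this criterion.

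The conclusion rests on two assumptions: that a site may reasonably apply the limits to the readings it takes at Visits 1 and 2, and that no site instruction outside these documents settles the matter.

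**What to change.** Replace no. 10 in Protocol 9.3.2 and in the Synopsis with:

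> Arterial hypertension, controlled or uncontrolled: (i) systolic >=140 mmHg and/or diastolic >=90 mmHg at eligibility assessment (measured per 9.6.3.7), or (ii) a current diagnosis of, or current drug treatment for, arterial hypertension according to the screening medical history (9.6.4.6), supported by the medication record, whatever the current readings.

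Limb (ii) should rest on the history. For prior medication, section 9.6.4.5 asks for start and stop dates; it lists the reason for use only for concomitant medication, from Visit 3 onward. The medication record can therefore support the history before enrolment but may not show why a drug was taken. Past hypertension that has resolved off treatment would remain a matter for the investigator under no. 42.

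The cost is one criterion reworded in two places and possibly a few more screen failures, among women whom the present wording already appears to mean to exclude. No new assessment is needed: history, medication and blood pressure are all recorded before the first dose.
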